8.2.1. Adverse Events of Special Interest

Adverse events of special interest (AESIs) are defined in [Table 12](#). The AESI checkbox on the CRF will not be considered or presented in summaries or data listings. AESIs are defined based on the FDA Medical Queries (FMQ) or Standardized MedDRA Queries (SMQ).

Table 12: Adverse Events of Special Interest

AESI	MedDRA Terms	Grades
Severe constipation (and/or severe, persistent, or worsening abdominal pain)	FMQ = Constipation FMQ = Abdominal Pain	Grade 3+
Diarrhea	FMQ = Diarrhea	Any Grade
Nausea and Vomiting	FMQ = Nausea FMQ = Vomiting	Grade 3+
Depression/other significant mood related disturbance (active suicidal ideation or behavior, severe depressive and/or anxious symptoms, other severe psychiatric TEAE)	FMQ = Depression FMQ = Anxiety FMQ = Psychosis	Grade 2+
Elevations in hepatic enzymes	SMQ = Liver related investigations, signs and symptoms (SMQ)	Grade 2+
Cardiac arrhythmia, related to an increase in QT/QTc interval.	SMQ = Torsade de pointes/QT prolongation (SMQ)	Any Grade

Other adverse events to be evaluated include Grade 3+ events of:

- Abdominal pain (FMQ) or Abdominal distension (HLT=Flatulence, bloating and distension)
- Elevations in INR defined by the MedDRA HLT = Coagulation and bleeding analyses

These adverse events are not defined as adverse events of special interest in the protocol but will be included in summaries of AESIs.

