Abbreviations: 5-HIAA = 5-hydroxyindoleacetic acid; BID = twice daily

Aside from the dose-dependent gastrointestinal TEAEs observed in healthy subjects receiving higher doses for 14 days, which have all been considered mild with the exception of 1 event of moderate diarrhea, no other safety concerns were identified following single doses ranging up to 2000 mg or following repeat dosing over 14 days of up to 800 mg administered BID to healthy subjects. The majority of TEAEs for all dose regimens evaluated to date have been mild and have resolved without requiring intervention or discontinuation of the IP. There have been no SAEs reported nor any dose-limiting toxicities identified. Mild, transient elevations in ALT were reported in 5 subjects who received either single or multiple doses of rodatristat ethyl (5 of 136 subjects [3.7%]). Further information can be found in the Investigator's Brochure.

With respect to nonclinical toxicology studies, rodatristat ethyl and rodatristat exposures at the no observed adverse effect level (NOAEL) in the 26-week rat (female only) or 39-week dog toxicology studies are > 4-fold higher than the expected exposure after at the higher dose regimen of 600 mg BID (IB, 2020). Due to adverse decreases in mean body weight gain (20 to -41.7% relative to controls) and food consumption at all dose levels in the 26-week study in male rats, the NOAEL could not be established. Exposure at the lowest dose tested in this study was 4-fold higher than that anticipated at the higher dose regimen of 600 mg BID. The major toxicities associated with oral rodatristat ethyl administration included mortality in rats preceded by clinical signs of toxicity and body weight loss occurring at exposures > 4-fold the highest exposure expected in the current study. Findings in both species were indicative of gastrointestinal changes including decreased body weight and/or decreased rate of weight gain, decreased food consumption, diarrhea/fecal change, dehydration, distended abdomen (rats only),

monitorable.

intestinal dilation with mucosal thickening and macrophage vacuolation (rats only), histopathologic findings of intestinal dilation with vacuolated macrophages, and increased mucosal thickness with regeneration in the duodenum. Observed liver enzyme elevations were not associated with adverse histopathology (hepatocellular necrosis) and are considered

Protocol RVT-1201-2002

Effective: 19JAN2022

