9.3.1. Adverse Events of Special Interest

AESIs include:

- Severe constipation (and/or severe, persistent, or worsening abdominal pain)
- Depression/other significant mood-related disturbance (active suicidal ideation or behavior, severe depressive and/or anxious symptoms, other severe psychiatric TEAE)
- Elevations in hepatic enzymes (see Appendix 3)
- Diarrhea (see Appendix 2)

9.3.2. Time Period and Frequency for Collecting Adverse Event, Adverse Events of Special Interest, Serious Adverse Event Information

All SAEs will be collected from the signing of the ICF until the Follow-Up Visit at the time points specified in the SoA (Section 1.3). All AEs will be collected from the first dose of IP.

Medical occurrences that begin before the start of IP but after obtaining informed consent will be recorded on the Medical History/Current Medical Conditions section of the eCRF not the AE section.

All SAEs will be recorded and reported to the Sponsor or designee immediately and under no circumstance should this exceed 24 hours, as indicated in Appendix 14. The Investigator will submit any updated SAE data to the Sponsor within 24 hours of it being available.

Adverse events of special interest must be reported to the Sponsor should they meet the definition of an SAE, and all timelines for reporting of SAEs should be adhered to.

Investigators are not obligated to actively seek AEs or SAEs after conclusion of study participation. However, if the Investigator learns of any SAE, including a death, at any time after a patient has been discharged from the study, and he/she considers the event to be reasonably related to the IP or study participation, the Investigator must promptly notify the Sponsor.

9.3.3. Method of Detecting Adverse Events, Adverse Events of Special Interest, and Serious Adverse Events

The method of recording, evaluating, and assessing causality of AEs and SAEs and the procedures for completing and transmitting SAE reports are provided in Appendix 14.

Care will be taken not to introduce bias when detecting AEs and/or SAEs. Open-ended and non-leading verbal questioning of the patient is the preferred method to inquire about AE occurrences.

9.3.4. Follow-up of Adverse Events, Adverse Events of Special Interest, and Serious Adverse Events

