 - Subject incidence of TEAEs leading to dose reduction by MedDRA SOC and PT. This is a subset of the AEs where Action Taken with Study Drug is checked as “Dose Reduced.”
 - Subject incidence of TEAEs leading to study drug interruption by MedDRA SOC and PT. This is a subset of the AEs where Action Taken with Study Drug is checked as “Drug Interrupted.”

The above summaries will be repeated where the adverse event is assigned to the dose the subject was taking at the time of the adverse event.

The following listings will be presented by treatment group and subject, include study day event started and the duration of event:

- All adverse events.
- AESIs (subset of the AEs where AE of Special Interest is marked as “Yes” or the AE meets the criteria specified in [Section 8.2.1](#)).
- Serious adverse events (subset of the AEs where serious is marked as “Yes”).
- CTCAE Grade 3 or higher adverse events (subset of AEs where severity is marked as CTCAE Grade 3, 4, or 5 or missing [to be presented as missing on the listing]).
- Related adverse events (subset of the AEs where relationship marked as “Related” or “Possibly Related” or missing relationship [to be presented as missing on the listing]).
- Adverse events leading to dose reduction (subset of the AEs where Action Taken with Study Drug is checked as “Dose Reduced”).

- Adverse events leading to study drug interruption (subset of the AEs where Action Taken with Study Drug is checked as “Drug Interrupted”).
- Adverse events leading to study drug discontinued (subset of the AEs where Action Taken with Study Drug is checked as “Drug Withdrawn”).
- Adverse events leading to discontinuation from the study (subset of the AEs where “Did the adverse event cause the subject to be discontinued from the study?” is “Yes”)
- Adverse events leading to death (subset of the AEs where outcome is indicated as “Fatal” or the CTCAE grade is 5 or seriousness criteria is Death).

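### SAP 8.2.1 and 8.2.3 contradict each other on the investigator's AESI flag, and Table 12 excludes persistent or worsening abdominal pain below Grade 3 although the protocol defines it as an AESI

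*SAP*

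**What the plan says.** **The flag.** SAP 8.2.1 states: "The AESI checkbox on the CRF will not be considered or presented in summaries or data listings". It defines AESIs instead by FDA Medical Queries or Standardized MedDRA Queries with a grade floor (Table 12). SAP 8.2.3 describes the AESI listing as "AESIs (subset of the AEs where AE of Special Interest is marked as" Yes, or where the event meets the 8.2.1 criteria.

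**Abdominal pain.** Protocol 9.3.1 lists "Severe constipation (and/or severe, persistent, or worsening abdominal pain" as one AESI. Protocol 8.1 uses the same three descriptors of pain in its mandatory withdrawal criteria. SAP Table 12 carries the protocol's label, assigns "FMQ = Constipation FMQ = Abdominal Pain", and sets the floor at Grade 3. Below the table, the SAP lists Grade 3+ abdominal pain or abdominal distension, and INR elevations, as further events for the AESI summaries. It says the protocol does not define these as AESIs.

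**Mood.** Protocol 9.3.1 lists "Depression/other significant mood-related disturbance (active suicidal ideation or behavior, severe depressive and/or anxious symptoms, other severe psychiatric TEAE". Table 12 repeats this label and assigns "FMQ = Depression FMQ = Anxiety FMQ = Psychosis" at Grade 2 or above.

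**The concern.** AESIs are the events the sponsor chose in advance to watch, so a reader of the report will take the AESI tables as the complete count by arm. Three features put that at risk.

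- The SAP gives two incompatible instructions on the flag. Two programmers could produce different listings, and one of those would not match the tables.
- A severity floor has been placed on an event that the protocol defines partly by its course over time. Persistence and worsening are not grades.
- One component named in the mood label, suicidal ideation or behavior, has no query of its own.

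Persistence and worsening are clinical judgments that a query plus a grade cannot reproduce. The investigator's flag is the field most likely to record them, and 8.2.1 sets it aside.

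**Working it through.** No sample size, power or event count bears on this point. The check sets the passages side by side.

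**1. The listing rule.** Cross the flag with the Table 12 criteria. *In* means the event appears.

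| Flag | Meets 8.2.1 criteria | AESI tables (8.2.1) | Listing under 8.2.1 | Listing under 8.2.3 |
|---|---|---|---|---|
| Yes | Yes | In | In | In |
| No | Yes | In | In | In |
| Yes | No | Out | Out | **In** |
| No | No | Out | Out | Out |

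The instructions differ in one cell: flagged events that no query and grade rule captures. Under 8.2.3 those events are listed but not tabulated. Under 8.2.1 they appear in neither output.

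**2. The abdominal pain row.** The protocol's three descriptors are joined by *or*, so any one is enough.

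| Pain event | AESI under protocol 9.3.1 | Enters the Table 12 row |
|---|---|---|
| Grade 3+ (taken as severe) | Yes | Yes |
| Grade 1-2, persistent | Yes | No |
| Grade 1-2, worsening but not reaching Grade 3 | Yes | No |
| Grade 1-2, neither | No | No |

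The two middle rows are excluded by construction. Because the flag is ignored, no other route brings them into the AESI tables.

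**3. The statement below Table 12.** It says Grade 3+ abdominal pain is not a protocol AESI. Protocol 9.3.1 names severe abdominal pain, and Table 12 already has a row for it at Grade 3+. The statement conflicts with both.

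**4. The mood row.** The label has three parts: suicidal ideation or behavior, severe depressive or anxious symptoms, and other severe psychiatric events. The queries named are depression, anxiety and psychosis. Suicidality enters only if its terms fall within one of those three, and the documents do not list their contents. SAP 8.6.1 plans C-SSRS listings only, so no table by arm fills a gap if there is one.

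**5. The other protocol AESIs.** Diarrhea is kept at any grade. Hepatic enzyme elevations get a Grade 2 floor that 9.3.1 does not state. That matters little: protocol Appendix 3 assigns no action at Grade 1, and SAP 8.3.3 and 8.3.4 summarise liver tests separately.

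**The case against.** **Nothing leaves safety reporting.** Every TEAE appears by arm in the SOC and preferred-term tables and in the all-AE listing, and pain that led to stopping drug appears in the discontinuation tables (SAP 8.2.3). This stands, and it limits the point to the AESI outputs.

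**A coded definition is legitimate.** The protocol does not describe the checkbox or make it part of the AESI definition. A uniform query rule is defensible, and the contradiction could also be removed by deleting the flag clause in 8.2.3. This stands too, so a mandatory rule counting any event that is flagged or captured by a query is not required. It does not answer the pain row, where the coded rule fails to reproduce its own label.

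**The SAP is not uniformly narrower.** Grade 3+ is a fair mapping of severe constipation. The mood queries start at Grade 2 although the protocol speaks of severe symptoms. Nausea and vomiting, QT-related arrhythmia, distension and INR are added. All of this is correct, and a reader should not infer that Table 12 narrows the AESIs across the board.

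**Other inferences the documents do not support.**

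- *That the IDMC would be misled.* The IDMC works under a separate charter, and nothing ties its outputs to Table 12.
- *That earlier healthy-subject experience shows the loss.* Protocol 4.7 describes those gastrointestinal events, "which have all been considered mild with the exception of 1 event of moderate diarrhea", as notably nausea and diarrhea. Table 12 keeps diarrhea at any grade, and nausea is not in protocol 9.3.1.
- *That suicidality is certainly lost.* This depends on query content not given. C-SSRS data are listed, with a separate listing of subjects reporting ideation and behavior, and HADS and QIDS-C category shifts are tabulated by arm (SAP 8.6).
- *That Section 11 conceals a change.* Protocol 10.4.2 plans no AESI summary, and Section 11 does say that safety analyses were added. A specific entry would be clearer, but the omission is a minor matter.

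**Conclusion.** Two errors stand on the text alone. SAP 8.2.1 and 8.2.3 give incompatible rules for the AESI listing. Table 12 excludes Grade 1-2 persistent or worsening abdominal pain from the AESI tables, although protocol 9.3.1 defines it as an AESI and 8.1 makes it a withdrawal criterion. The SAP's remark that abdominal pain is not a protocol AESI is also wrong. The missing suicidality mapping is an ambiguity to resolve, not a shown loss.

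The size cannot be stated as a rate. The under-count in the pain row equals the number of subjects whose only qualifying pain event is Grade 1-2 and persistent or worsening. That could be none or several, and the documents give no data to say which. The effect is confined to the AESI outputs. The conclusion assumes that severe corresponds to Grade 3 or above and that the protocol's three descriptors are alternatives, as its wording indicates. It should be corrected, since a stated rule would under-count a protocol-defined AESI and the needed data are already collected.

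**What to change.** 1. Make 8.2.1 and 8.2.3 agree on the flag. One workable form keeps the query-based definition for the tables, limits the 8.2.1 sentence to those tables, and shows investigator-flagged events that no query captures in a supportive table or listing, labelled as such.
2. Present abdominal pain at all grades beside Grade 3+. All-grade counts will include some pain that was neither persistent nor worsening, so the footnote should say so. Constipation can stay at Grade 3+.
3. Map suicidal ideation or behavior to a named query or an explicit term list, or state that the depression query contains those terms.
4. Correct the statement that Grade 3+ abdominal pain is not a protocol AESI, and remove the duplicate entry.
5. Record the change in SAP Section 11, or in the CSR as SAP Section 1 allows.

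The cost is SAP wording and some table programming, with no new data collection. AESI counts will be slightly higher.

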8.2.2. Overall Summary of Adverse Events

The number and percentage of subjects who experience at least one of the following:

- Any TEAE, All CTCAE grades
- Any TE AESI
- Grade 3+ TEAE
- TEAE by Maximum CTCAE Grade
- Serious TEAE
- TEAE leading to death

- Treatment-related TEAE, All CTCAE grades
- TEAE by highest relationship
- Treatment-related Grade 3+ TEAE
- Treatment-related serious TEAE
- TEAE leading to dose modification
 - TEAE leading to dose reduction
 - TEAE leading to study drug interruption
 - TEAE leading to study drug discontinued
- TEAE leading to discontinuation from the study

As subjects were allowed to dose reduce and hold, this summary will be repeated where the adverse event is assigned to the dose the subject was taking at the time of the adverse event. AEs will be determined to have occurred on a dose (0 mg/placebo, 300 mg, 600 mg) based on the adverse event start date. For example, if the adverse event starts on or after the start of the first dose, before any dose reduction, the adverse event will be counted as occurring during the first dose. If a subject dose reduces (0 mg/placebo or 300 mg) and the adverse event starts after the dose reduction/start of the second dose, the adverse event will be counted as occurring on the second dose. If the AE occurred after the last dose, the AE will be assigned to the last dose taken. The denominator for percentages is the number of subjects who ever took the specified dose.

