- Total number of dose tablets expected= [dose reduction treatment duration $\times 2$ (tablets per day)] + [treatment duration without reduction or interruption $\times 4$ (tablets per day)]
where dose reduction treatment duration is calculated as the sum from all dose adjustments of the number of days between the dose adjustment start date and dose adjustment end date and the treatment duration without any dose reduction or dose interruption is the sum of these durations number of days from start to end dates.

Dose interruptions resulting drug withdrawal will have a missing end date, and the date of last dose will be used. Subjects who continue into the OLE on a dose reduction may have a missing end date, the day before the first OLE dose will be used.

Treatment compliance will be summarized using descriptive statistics for the Safety population. In addition, the overall treatment compliance will be further categorized as < 80%, 80% – 100% and > 100%, and the number and percentage of subjects with compliance in each category will be presented.

Study drug administration including drug interruptions, dose reductions, overdoses, and study drug dispensing and accountability, calculated durations of exposure, and calculated compliances will be presented in by-subject data listings.

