8.2. Adverse Events

Adverse events will be coded using Medical Dictionary for Regulatory Activities (MedDRA) each verbatim term coded to a lower level term (LLT) which is mapped to a preferred term (PT), high level term (HLT), high level group term (HLGT), and a system organ class (SOC). AE severity and intensity using the National Cancer Institute Common Terminology Criteria for Adverse Events (NCI CTCAE, Version 5) are recorded on the eCRF. Both will be presented in listings, CTCAE grade will be used in summaries and analyses.

Adverse event summaries will summarize only treatment-emergent AEs (TEAEs), which are defined as AEs not present prior to the start of study medication, or AEs present before study medication that worsened after starting study medication. If a partially missing date or time of onset allows the possibility that an AE may be a TEAE it will be assumed that it is a TEAE. Each AE will be assigned to the most recent treatment received AEs with a start on or after the first OLE dose will be assigned to the OLE treatment phase and not included in the main study AE analyses. For subjects who discontinued study without going to the open label extension, AEs started after first dose and within the 28 days of last dose will be counted as TEAEs. If it cannot be determined whether an AE is treatment emergent due to a partial onset date, then it will be counted as such. Methodology for imputation of partial AE start and stop dates is described in [Appendix 1](#). Each summary will be displayed by treatment group, including Total Rodatristat ethyl and Overall.

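### The by-dose adverse event tables pool randomized placebo patients with active-arm patients most likely reduced to 0 mg, so the 0 mg/placebo column is not a clean placebo rate

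*SAP*

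**What the plan says.** SAP 8.2 presents the main adverse event summaries by treatment group. SAP 8.2.2 then adds a second set: "As subjects were allowed to dose reduce and hold, this summary will be repeated where the adverse event is assigned to the dose" in use at onset. Four rules define it.

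- Levels: "AEs will be determined to have occurred on a dose (0 mg/placebo, 300 mg, 600 mg) based on the adverse event start date".
- Reductions: "If a subject dose reduces (0 mg/placebo or 300 mg) and the adverse event starts after the dose reduction/start of the second dose", the event is counted on that second dose.
- After stopping: "If the AE occurred after the last dose, the AE will be assigned to the last dose taken".
- Denominator: "The denominator for percentages is the number of subjects who ever took the specified dose".

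SAP 8.2.3 extends this to the incidence tables: "The above summaries will be repeated where the adverse event is assigned to the dose the subject was taking" at onset. For patients who do not enter the extension, SAP 8.2 sets the reporting window: "AEs started after first dose and within the 28 days of last dose will be counted as TEAEs".

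Protocol 4.3 and Table 3 give the tablets. Every patient takes two per intake, twice daily: two active (600 mg arm), one active and one placebo (300 mg arm), or two placebo. The only active strength is 300 mg. Protocol 4.4.1 allows one level of reduction, to a single tablet per intake from designated bottles, and leaves the bottle details to separate instructions.

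**The concern.** The by-dose tables describe which events occurred on which dose. If the lowest level holds both patients who never received active drug and patients who moved to placebo tablets after taking active drug, its percentage estimates neither group's rate.

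The added patients are not a random sample. Protocol 4.4.1 offers reduction mainly to manage adverse events, naming gastrointestinal events and liver enzyme increases. SAP Table 12 lists diarrhea of any grade and hepatic enzyme elevations of Grade 2 or above as events of special interest. Patients would thus enter the pooled level largely because of the kinds of event the tables report. The percentage could move either way: a short time at 0 mg gives little opportunity for a new event and lowers it, while intolerance or recent drug exposure raises it.

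**Working it through.** The plan gives no figure on this point to reproduce. The check has two parts: who can fall in the level, and how far a few such patients could move its percentage.

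**1. Who falls in the 0 mg/placebo level**

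| Arm | Full intake | One-tablet intake | Level when reduced |
|---|---|---|---|
| 600 mg | 2 active | 1 active | 300 mg |
| 300 mg | 1 active + 1 placebo | 1 placebo (inferred) | 0 mg/placebo |
| Placebo | 2 placebo | 1 placebo | 0 mg/placebo |

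Only the middle row needs an inference. If the retained tablet were the active one, a 300 mg patient would still receive 300 mg and would not have been reduced. The SAP also names 0 mg/placebo as one of the two levels a reduced patient can move to. Placebo tablets only is therefore the natural reading, but neither document states it.

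**2. A route that follows from the protocol**

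Protocol Appendix 3 permits a one-pill twice-daily reduction for ALT or AST from 3 to below 5 times the upper limit of normal. It requires permanent discontinuation if values are still at least 3 times that limit after two weeks. If the retained pill is placebo, a 300 mg patient on this path has 0 mg as the last dose. New events in the following 28 days are then assigned to 0 mg/placebo, although the patient was stopped for a possible liver effect of the drug.

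**3. Size, by illustration**

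Inputs: 30 placebo patients (planned arm size, SAP 3) and 168 treatment days (24 weeks). Assumed, because the documents give no rates: 3 placebo patients have the event, k = 1 to 3 reduced 300 mg patients enter the level, and y of these k have the event there.

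Column rate = (3 + y) / (30 + k). Randomized placebo alone: 3/30 = 10.0%.

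| k | None of the k has it (y = 0) | All of the k have it (y = k) |
|---|---|---|
| 1 | 3/31 = 9.7% | 4/31 = 12.9% |
| 2 | 3/32 = 9.4% | 5/32 = 15.6% |
| 3 | 3/33 = 9.1% | 6/33 = 18.2% |

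With k = 0 the rate stays at 10.0%.

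**4. Weight in the denominator against time at risk**

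Assume three reductions of 28 days each; Appendix 2 allows re-escalation within 4 weeks after a reduction for diarrhea.

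- Share of subjects: 3/33 = 9.1%.
- Placebo patient-days: 30 × 168 = 5,040. Added days: 3 × 28 = 84. Share of time: 84/(5,040 + 84) = 1.6%.

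These patients would thus be 9.1% of the denominator with 1.6% of the observation time.

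**5. Carry-over**

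Protocol 2.1 gives a half-life of about 12 hours for rodatristat. Five half-lives are 5 × 12 = 60 hours, or 2.5 days, which is 2.5/28 = 8.9% of a 28-day reduction. Residual drug thus matters only early in a reduction of that length. Selection by earlier events and the short time at risk are the larger reasons for the lack of comparability.

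**The case against.** The strongest reply is that mixing is what an as-dosed table does. Placebo is 0 mg of active drug, the SAP does not name this column as a comparator, and the 300 mg column likewise mixes randomized 300 mg patients with reduced 600 mg patients. SAP 8 rules out inferential safety comparisons, the by-arm tables keep placebo unmixed, and the listings and the swim-lane figure show individual cases. The bottle content is also unseen.

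Most of this stands, and it limits the point to a minor one. It does not remove it. Reduced 600 mg patients in the 300 mg column did take 300 mg, so that label is accurate; the 0 mg/placebo label hides which patients are randomized controls.

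Three stronger readings are tempting, and the documents do not support them.

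- A reader might infer that temporary holds also count as 0 mg, since "As subjects were allowed to dose reduce and hold, this summary will be repeated where the adverse event is assigned to the dose" mentions holds. But SAP 8.2 assigns each event to the most recent treatment received, the denominator counts doses taken, and the examples in 8.2.2 cover reductions only. Held patients more plausibly stay with their active dose. Nor can a difference between holds that end in restart and holds that end in withdrawal be drawn from "Dose interruptions resulting drug withdrawal will have a missing end date, and the date of last dose will be used", because that rule belongs to the compliance calculation in 8.1.
- A reader might infer that the interruption-adjusted exposure duration in 8.1 overstates exposure by including 0 mg days. SAP 2.2.2 defines study drug to include placebo, so placebo-tablet days belong in that duration. Active exposure has its own measure, total milligrams, which would give zero for those days.
- A reader might take 0 mg/placebo as the designated reference for the by-dose tables. The SAP does not say so.

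**Conclusion.** The concern holds as a minor one. As written, the by-dose rules most likely place reduced 300 mg patients in the same level as randomized placebo patients, give each of them full weight in the denominator, and send their events after a 0 mg last dose to that level. The resulting percentage should not be read as a placebo rate.

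This rests on the inference that the reduced 300 mg intake contains no active tablet. The direction and size are unknown. The range of 9.1% to 18.2% against 10.0% is illustrative and depends on three such patients and an assumed 10.0% placebo rate; there is no effect if no such patients occur. A reader might go further and doubt the placebo rates throughout the safety report. That does not follow, because the by-arm tables are unaffected.

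**What to change.** In the by-dose tables of SAP 8.2.2 and 8.2.3, replace the single lowest level with two columns.

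- *Placebo (randomized)*: patients treated in the placebo arm, with that number as denominator.
- *0 mg, active arms*: active-arm patients who took a 0 mg reduced dose, with their own number as denominator. If such a patient's last dose was 0 mg, events after it go in this column.

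The cost is one sparse column, fit for description only, and one or two SAP sentences. No new data are needed: treatment assignment and dose-adjustment dates are already required to build these tables.
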